3.7.2 Control Group

- Subjects will receive standard antenatal care and follow-up plan similar to the intervention group.

Primary outcome

- Systolic and diastolic blood pressure, which will be measured at rest using sphygmomanometer twice on both arms by research nurses during daytime ANC at 10:00-12:00 pm at randomization (GA 0-16 week), 1.5-2 month after randomization (GA 18-20 week), and 3-4 month after randomization (GA 24-28 week), 5-6 month after randomization (GA 32-34 week) and monthly (GA>35 week) until delivery

Secondary outcome

- 24-hour ambulatory blood pressure monitoring (daytime versus night time) using the non-invasive technique from pulse transit time (SomnoTouch NIBP).
- Pregnancy complication listed as composite endpoints below

(Composite endpoint): A combination of clinical endpoints in maternal and fetal outcomes, data from Ramathibodi hospital during 2013-2014) *

- **Composite 1:** hypertensive disorder of pregnancy;
- **Composite 2:** hypertensive disorder of pregnancy or preterm labor or fetal growth restriction
- **Composite 3:** Preterm labor or fetal growth restriction, or severe pre-eclampsia or eclampsia or death; (composite 3 incidence=10%)

*Given that the incidence of hypertensive disorder incidence= $136/3787=3.6\%$;
gestational diabetes incidence= $601/3787=15.9\%$; fetal growth restriction incidence= $157/3787=4.1\%$; preterm labor incidence=10%; and severe pre-eclampsia/eclampsia/HELLP syndrome incidence= $(43+ 1+3=46/3787=1.2\%)$, respectively.

- Individual component of the composite endpoints including incidence of hypertensive disorder of pregnancy, gestational diabetes, preterm labor, and fetal growth restriction
- Glucose level, Oral Glucose Tolerance Test (OGTT), HbA1C
- Fetal ultrasound results: uterine Doppler arterial blood flow, fetal growth restriction
- Neonatal outcome: birth-weight, APGAR score, Length of stay, NICU admission

- Placenta character: weight will be measured at birth by the neonatal nurse.

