1.1 Background and rationale

1.1.1 Magnitude of problem:

Obstructive sleep apnea (OSA) is caused by the cyclical upper airway collapses during sleep resulting in arousals, sleep fragmentation, intermittent oxygen desaturation, and sympathetic activation [1]. The prevalence of OSA in general population varied from approximately 2% to 26% worldwide [2, 3]. Prevalence of OSA in general population approximates 4% in men, and 2% in women [2]. Similarly, the prevalence of OSA in Thai population approximates 4.3-4.4% (5.3-15% male; 1.9-3.9% female) [4, 5]. However, it has been estimated that up to 93% of women and 82% of men with moderate to severe OSA have still remained undiagnosed [6]. The prevalence of sleep disordered breathing (SDB) in high-risk pregnancy was also high, which ranged from 20% to 35% (16-21) as for diagnosis based on objective sleep tests (e.g., polysomnography (PSG) or Watch-PAT) [7-12]. Recent meta-analysis showed the pooled prevalence of SDB during pregnancy of 26.7% (95%CI: 16.9%, 34.4%, $I^2=83.15%$) [13]. However, prevalence of SDB in pregnancy remains uncertain depending on various factors such as population studied (high vs low risk), type of diagnostic measures, and trimester of study.

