3. METHODOLOGY

3.1 Study design and setting

The study design will be a multicenter randomized-controlled trial in 3 tertiary care hospitals including Ramathibodi Hospital, Phramongkutklao Hospital and Rajavithi Hospital.

3.1.1 Ramathibodi Hospital is a [university hospital](#) of the Faculty of Medicine Ramathibodi Hospital which is a faculty within [Mahidol University](#) and the fourth oldest medical school in Thailand. The hospital serves at least 5,000 out-patient visits per day and in-patients with more than 1,000 beds for tertiary medical care. The hospital provides approximately 3,000 antenatal care service and delivery each year. It will be the primary site of the research investigation. The study will initiate here in June 2016 and followed by other centers. The study will take approximately 2 years for the accrual time to achieve the target number of participants and another year for the completion and analysis.

3.1.2 Phramongkutklao College of Medicine is the first and only medical cadet school in [Thailand](#). The college is the seventh medical school established in Thailand by the will of [King Bhumibhol Adulyadej](#). Phramongkutklao College of Medicine is an affiliated college of [Mahidol University](#). It is the teaching hospital accommodating 1,200-bed in the tertiary level. The hospital provides approximately 3,000 antenatal care service and delivery each year. The research will start soon after the study initiation in Ramathibodi Hospital once the ethics committee and funding are approved. The study will take approximately 2 years for the accrual time to achieve the target number of participants and another year for the completion and analysis.

3.1.3 Rajavithi Hospital is a 1,200-bed medical center accommodating 40,000 in-patients and 1,000,000 out-patients yearly or a daily average of 4,000 patients, with 200,000 referral patients (both in and out patients). The hospital provides medical service at standard health promotion in tertiary levels and above, including quality referral system. The hospital provides approximately 4,000 antenatal care service and delivery each year. The research will start soon after the study initiation in Ramathibodi Hospital once the ethics committee and funding are approved. The study will take approximately 2 years for the accrual time to achieve the target number of participants and another year for the completion and analysis.

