3.2.1 Inclusion criteria (ALL criteria)

- Singleton pregnant women age ≥ 18 years without significant medical conditions such as immunocompromised status, chronic infection (HIV infection, tuberculosis), chronic lung and cardiac conditions, chronic kidney disease, thyroid disease, or neuromuscular disease.
- Pregnant women attending the 1st antenatal care and intending to deliver at one of the study hospitals with gestational age < 16 weeks
- Thai nationality with ability to use Thai language proficiently both in spoken and written language.
- Have been diagnosed as high-risk pregnancy by obstetricians by having any of the following conditions

- a. Chronic hypertension prior to pregnancy
- b. Hypertension during pregnancy before 20week gestation.
- c. Pre-eclampsia/gestational hypertension during recent pregnancy
- d. Obesity defined by pre-pregnancy body mass index (BMI) ≥ 27.5 kg/m²
- e. Having diabetes mellitus or history of gestational diabetes in previous pregnancy
- Having SDB by either definition
 - a) RDI ≥ 5 events/hour by sleep testing at either point of testing during early pregnancy (0-16 GA week) or late pregnancy (GA 24-28 week)
 - b) OR Presence of snoring (either as frequent snoring ≥ 3 times/week or loud snoring) prior to or occurring during pregnancy
- Sign written informed consent

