3.9.2 Based on composite endpoint

Sample size calculation is also done according to the composite endpoint.

- **Composite 1 (hypertensive disorder of pregnancy)**

For composite endpoint 1, sample size of 134 each arm is required to detect difference of 15% with type I and II error of 0.05 and 0.20 respectively. Therefore, given the sample size of 153 each arm from the primary endpoints, it is possible to include this composite endpoint.

- **Composite 2 (hypertensive disorder of pregnancy or preterm labor or fetal growth restriction or emergency C/S)**

For composite endpoint 2, sample size of 141 each arm is required to detect the difference of 15% with type I and II error of 0.05 and 0.20 respectively. Therefore, given the sample size of 153 each arm from the primary endpoints, it is possible to include this composite endpoint.

And given the limitation in number of participant enrollment (n=306), estimation of the power of the study based on the effect size of the CPAP on composite endpoint 2 are done below. To achieve a difference of 12% and 15% on the composite endpoint 2, given the sample size of 306, it will achieve the power of 0.83 and 0.97, respectively.

- **Composite 3**

For composite endpoint 3, sample size of 492 each arm is required to detect difference of 6% with type I and II error of 0.05 and 0.20 respectively. Therefore, given the sample size of 153 each arm from the primary endpoints, it is **Not** possible to include this composite endpoint.

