### **Secondary outcome**

- 24-hour ambulatory blood pressure monitoring (daytime versus night time) using the non-invasive technique from pulse transit time (SomnoTouch NIBP).
- Pregnancy complication listed as composite endpoints below

**(Composite endpoint):** A combination of clinical endpoints in maternal and fetal outcomes, data from Ramathibodi hospital during 2013-2014) \*

- **Composite 1:** hypertensive disorder of pregnancy or gestational diabetes; (composite1 incidence= $699/3787=18.5\%$ )
- **Composite 2:** hypertensive disorder of pregnancy or gestation diabetes or preterm labor or fetal growth restriction (composite 2 incidence = $812/3787= 21.4\%$ )
- **Composite 3:** Preterm labor or fetal growth restriction, or severe pre-eclampsia or eclampsia or death; (composite 3 incidence= $10\%$ )

\*Given that the incidence of hypertensive disorder incidence= $136/3787=3.6\%$ ; gestational diabetes incidence=  $601/3787=15.9\%$ ; fetal growth restriction incidence=  $157/3787=4.1\%$ ; preterm labor incidence= $10\%$ ; and severe pre-eclampsia/eclampsia/HELLP syndrome incidence= ( $43+ 1+3=46/3787=1.2\%$ ), respectively.

- Individual component of the composite endpoints including incidence of hypertensive disorder of pregnancy, gestational diabetes, preterm labor, and fetal growth restriction
- Glucose level, Oral Glucose Tolerance Test (OGTT), HbA1C
- Fetal ultrasound results: uterine Doppler arterial blood flow, fetal growth restriction
- Neonatal outcome: birth-weight, APGAR score, Length of stay, NICU admission
- Placenta character: weight will be measured at birth by the neonatal nurse.

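### The powers of 0.83 and 0.97 for composite 2 rest on a one-hospital rate of 21.4% that included gestational diabetes, and are not supported for the high-risk women and the endpoint now analysed

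*Protocol*

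**What the plan says.** Section 3.7.2 of the Protocol and the Secondary outcome section of the Combined protocol and SAP describe the composites as "A combination of clinical endpoints in maternal and fetal outcomes, data from Ramathibodi hospital during 2013-2014", with denominator 3787. The Combined protocol and SAP includes GDM in composites 1 and 2 and gives hospital rates of 699/3787 = 18.5% and 812/3787 = 21.4%; the second follows the definition ending "preterm labor or fetal growth restriction (composite 2 incidence". The Protocol removes GDM from both composites (3.7.2, and again in 3.10.4) and prints no new rate for either. Composite 3 is 10% in both documents.

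Section 3.9.2 of the Protocol nevertheless carries the same figures as the Combined protocol and SAP:

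- 134 per arm (composite 1, difference of 15%) and 141 per arm (composite 2, 15%), both judged possible with 153 per arm;
- 492 per arm (composite 3, 6%), judged not possible;
- for composite 2 at differences of 12% and 15%, "given the sample size of 306, it will achieve the power of 0.83 and 0.97, respectively".

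Entry is restricted. Under 3.2.1, women must "Have been diagnosed as high-risk pregnancy by obstetricians by having any of the following conditions" (chronic or early hypertension, recent pre-eclampsia or gestational hypertension, obesity, diabetes or past GDM), and must also have SDB by sleep test or snoring.

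**The concern.** A power statement for a difference in proportions is only as good as its control rate. Here the rate appears to describe all deliveries at one hospital, whereas the trial selects women for conditions that raise the risk of these outcomes. Section 1.1.2 adds that SDB is itself associated with gestational hypertension, pre-eclampsia and low birth weight. No adjustment of the hospital rates is described. The endpoint has changed as well: 21.4% belongs to a composite that is no longer analysed.

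At stake is how a null composite 2 result would be read. With a stated power of 0.83 or 0.97 it looks like fair evidence against an effect of that size. If the power is not known, it is not.

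**Working it through.** **Inputs.** Two-sided alpha 0.05, 1:1 allocation and 80% power for the sample sizes (Protocol 3.9.1, 3.9.2, 3.10.4); 153 per arm (3.9.2); 139 per arm before loss and 167 per arm enrolled (Protocol 3.9.1); hospital rates as above.

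**Formulas.** With arm rates p1 and p2, their mean p̄, difference d and n per arm, using pooled variance under the null and no continuity correction:

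- power = Φ{[d√n − 1.960·√(2p̄(1−p̄))] / √(p1(1−p1) + p2(1−p2))}
- n = [1.960·√(2p̄(1−p̄)) + 0.842·√(p1(1−p1) + p2(1−p2))]² / d²

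**1. The printed powers reproduce as falls from 21.4%.**

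- 21.4% to 9.4%: p̄ = 0.154 and d√153 = 1.484, so (1.484 − 1.960 × 0.5105)/0.5034 = 0.961, power 0.832.
- 21.4% to 6.4%: p̄ = 0.139 and d√153 = 1.855, so (1.855 − 1.960 × 0.4892)/0.4776 = 1.877, power 0.970.

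A continuity correction (0.788/0.956), a one-sided test (0.900/0.986) or a rise from 21.4% (0.654/0.828) does not match both figures.

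**2. The printed sample sizes reproduce with the hospital rate as the lower arm.**

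| Composite | Printed n | Hospital rate as lower arm | Fall from hospital rate |
|---|---|---|---|
| 1, 15 points | 134 | 18.5% vs 33.5%: 134 | 18.5% vs 3.5%: 68 |
| 2, 15 points | 141 | 21% vs 36%: 141 (21.4% vs 36.4%: 143) | 21.4% vs 6.4%: 83 |
| 3, 6 points | 492 | 10% vs 16%: 492 | 10% vs 4%: 283 |

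So 3.9.2 uses the rate in opposite directions. It asks for 141 per arm for 80% power at 15 points, yet claims 0.97 at 15 points with 153.

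**3. Who the 21.4% describes.** The documents state no risk restriction on the 3787. Section 3.1.1 says of this hospital: "The hospital provides approximately 3,000 antenatal care service and delivery each year". A series larger than a full year's deliveries is hard to read as a high-risk subset.

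**4. What dropping GDM does.** The remaining component rates in 3.7.2 are 3.6% (hypertensive disorder), 10% (preterm labor) and 4.1% (fetal growth restriction). The GDM-free composite 2 in that series therefore lies between 10% (complete overlap) and 3.6 + 10 + 4.1 = 17.7% (no overlap). Composite 1 falls to 3.6%, from which a 15-point reduction is impossible. Section 3.9.2 also lists emergency caesarean under composite 2; 3.7.2 does not, and no rate is given for it.

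**5. Sensitivity, absolute differences kept.** The control rates from 25% upwards are assumptions.

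| Control rate | 12 / 15 points, 153 per arm | 12 / 15 points, 139 per arm |
|---|---|---|
| 21.4% | 0.83 / 0.97 | 0.80 / 0.96 |
| 25% | 0.77 / 0.94 | 0.73 / 0.91 |
| 30% | 0.69 / 0.89 | 0.65 / 0.85 |
| 35% | 0.64 / 0.84 | 0.60 / 0.80 |
| 40% | 0.60 / 0.80 | 0.56 / 0.76 |
| 50% | 0.56 / 0.76 | 0.52 / 0.72 |

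With 153 per arm, 12-point power drops below 0.80 above a control rate of about 23%, and 15-point power above about 40%.

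**6. Sensitivity, relative reduction kept.** The implied reductions are 12/21.4 = 56% and 15/21.4 = 70%. With 153 per arm, power is 0.74/0.93 at a control rate of 17.7%, 0.95/0.997 at 30% and 0.99/1.00 at 40%.

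**7. Composite 3.** At control rates of 20% and 40% (assumed), a 6-point fall needs about 614 and 1015 per arm. Even 10% to 4% needs 283, against 153.

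**The case against.** The strongest reply is that nothing here shows the printed powers to be too high. A reader might infer from the enrichment that true power must be lower. The documents do not support that, for two reasons. First, no high-risk rate is given. With GDM removed, the hospital rate for composite 2 is only 10% to 17.7%, so an enriched rate could lie near 21.4%, where 0.83 and 0.97 hold at 153 per arm, or slightly below it, where power for a fixed difference is higher. Second, the loss requires a fixed absolute difference; with a fixed relative reduction, enrichment raises power. Both points stand. They leave the control rate unsupported all the same: agreement with 21.4% would be coincidence.

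A reader might also infer that the feasibility verdicts fall. They largely do not. The sample sizes pair the hospital rate with a higher one; if that is the control arm, they already assume about 33.5% to 36% for composites 1 and 2. It is likewise tempting to read 141 as a 12-point fall, since 21.4% to 9.4% gives 141 too. But the Protocol labels it 15%, and the lower-arm reading reproduces all three sample sizes at their printed differences.

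Nor should chronic hypertension at entry be counted as an outcome event. Section 2.1 lists it among the hypertensive disorders, but the secondary objective names pre-eclampsia and gestational hypertension.

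Finally, the composites are secondary and the trial is sized on blood pressure. That limits the consequence but does not justify the printed powers.

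**Conclusion.** The powers of 0.83 and 0.97 are arithmetically correct for a 21.4% control rate with 153 per arm, but the documents do not support that rate for the women enrolled or for composite 2 as now defined. That the 3787 are unselected deliveries is an inference, though a strong one.

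The size of the discrepancy cannot be fixed from the documents. Over assumed control rates of 25% to 50%, with absolute differences kept and 153 per arm, power is 0.77 to 0.56 for 12 points and 0.94 to 0.76 for 15 points. The 12-point statement is fragile, losing 80% power less than two points above 21.4%. With a fixed relative reduction the movement is upwards.

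For composite 2, the conclusion that a 15-point fall is detectable survives up to a control rate of about 40% with 153 per arm, or about 35% with 139. Composite 3 remains out of reach for a 6-point fall. The opposite use of the base rate within 3.9.2 is an internal inconsistency whatever the true rate. The primary endpoint is unaffected. This should be corrected, but it does not threaten the trial.

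**What to change.** In Protocol 3.9.2:

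1. State the assumed control-arm rate of each composite as currently defined, without GDM, in high-risk women. Take it from the same 2013-2014 records restricted to entry conditions a to e or, if these cannot be separated, from the trial's own pooled rate without regard to arm. Show a range around it.
2. Say whether the effect is an absolute or a relative reduction.
3. Recompute all sample sizes and powers in one direction, as a fall from the control rate, with the numbers in 3.9.1 (139 per arm evaluable, 167 enrolled) in place of 153. Re-derive the possible and not-possible statements from the same rates.
4. Replace the 0.83/0.97 sentence. If absolute differences are kept, it could read: with 139 per arm, power for falls of 12 and 15 points in composite 2 is 0.73/0.91, 0.65/0.85 and 0.56/0.76 at assumed control rates of 25%, 30% and 40%.
5. Make the component list of composite 2 agree between 3.7.2 and 3.9.2.

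The cost is a re-tabulation of records already used, or of pooled trial data, and one rewritten section. Enrolment does not change. The downside is that the stated power may become less favourable.

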1.2 Research Question

1.2.1 Does the use of CPAP treatment for SDB in pregnant women with preeclampsia risk result in better blood pressure control and thus reduce related maternal and fetal complications than standard usual antenatal care in control group

1.2.2 We want to investigate whether our proposed screening algorithm for SDB specific to pregnancy is accurate and feasible in monitoring and diagnosis of SDB during pregnancy.

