1.3 Research Objectives

1.3.1 **Primary Objective:** To compare whether the treatment effect of CPAP on SDB during pregnancy can improve blood pressure control in high risk pregnancy

- Systolic/diastolic blood pressure during daytime ANC at 10:00-12:00 am at randomization (GA 0-16 week), 1.5-2 month after randomization (GA 18-20 week), and 3-4 month after randomization (GA 24-28 week), 5-6 month after randomization (GA 32-34 week) and monthly (GA>35 week) until delivery

1.3.2 **Secondary Objective:**

- To compare the composite outcome of pre-eclampsia/GHT, GDM, fetal growth restriction, and pre-term labor between the CPAP treatment and control groups. And individual outcomes.
- To compare the night-time blood pressure compared to control group. 2nd outcome

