2.1 Definitions

Obstructive sleep apnea (OSA)/Sleep disordered breathing (SDB)/Upper airway resistance syndrome (UARS): Diagnostic criteria according to the International Classification of Sleep Disorders. 3rd Edition includes (A and B) or C satisfy the criteria [28]

A. The presence of 1 or more of the following:

1. The patients complain of sleepiness, nonrestorative sleep, fatigue, or insomnia symptom
2. The patient wakes with breath holding, gasping, or choking
3. The bed partner or other observer reports habitual snoring, breathing interruptions, or both during the patient's sleep.
4. The patient has been diagnosed with hypertension, a mood disorder, cognitive dysfunction, coronary artery disease, stroke, congestive heart failure, atrial fibrillation, or type 2 diabetes mellitus

B. PSG or out-of-center sleep test (OCST) demonstrates:

1. 5 or more predominantly obstructive respiratory events (obstructive and mixed apneas, hypopneas, or respiratory effort related arousal (RERAs) per hour of sleep during a PSG or per hour of monitoring (OSCT).

OR

C. PSG or OCST demonstrates:

1. 15 or more predominantly obstructive respiratory events (obstructive and mixed apneas, hypopneas, or respiratory effort related arousal (RERAs) per hour of sleep during a PSG or per hour of monitoring (OSCT).

Apnea: a reduction of thermistor signal at least 90% from baseline lasting for at least 10 seconds. Obstructive apnea is classified by the presence of RIP effort, and central apnea is classified by the absence of RIP effort [18].

Hypopnea: a reduction in nasal pressure transducer signal at least 30% from baseline that is associated with either O₂ desaturation $\geq 3\%$ from baseline or EEG arousal.

Respiratory effort related arousals (RERA): a sequence of breaths lasting ≥ 10 seconds characterized by increasing respiratory effort or by flattening of the inspiratory portion of the nasal pressure leading to arousal from sleep that does not meet the criteria for apnea or hypopnea.

Apnea-hypopnea index (AHI): = no. of apnea+hypopnea events/Total sleep time (hr)

Respiratory disturbance index (RDI): no. of apnea+hypopnea+RERA/Total sleep time (hr)

Hypertensive disorder of pregnancy consisted of 4 categories [29]

a) **Preeclampsia-eclampsia:** diagnostic criteria includes

▪ **Blood pressure:**

- $\geq 140/90$ mmHg on 2 occasions at least 4 hours apart after 20 weeks of gestation in a woman with a previously normal blood pressure

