- $\geq 160/110$ mmHg, hypertension can be confirmed within a short interval (minutes) to facilitate timely antihypertensive therapy

And

▪ **Proteinuria**

- ≥ 300 mg per 24-hour urine collection (or this amount extrapolated from a timed collection) OR
- Protein/creatinine ratio ≥ 0.3 (each measured as mg/dL)
- Dipstick reading of 1+ (used only if other quantitative methods not available)

Or in the absence of proteinuria, new-onset hypertension with the new onset of any of the following:

- **Thrombocytopenia**
 - Platelet count $<100,000$ /microliter
 - **Renal insufficiency**
 - Serum creatinine concentration > 1.1 mg/dL or a doubling of the serum creatinine concentration in the absence of other renal disease
 - **Impaired liver function**
 - Elevated blood concentrations of liver transaminases to twice normal concentration
 - **Pulmonary edema**
 - **Cerebral or visual symptoms**
- b) Chronic hypertension (of any cause)** is hypertension that predates pregnancy
- c) Chronic hypertension with superimposed preeclampsia** is chronic hypertension in association with preeclampsia
- d) Gestational hypertension** is BP elevation after 20 weeks of gestation in the absence of proteinuria or the aforementioned systemic findings.

- **Two-step strategy**

- **Step 1:** perform 50-g GLT (nonfasting), with plasma glucose measurement at 1 h, at 24-28 weeks of gestation. If plasma glucose level at 1 hour after the load is 140 mg/dL, proceed to a 100-gm OGTT.
- **Step 2:** the 100-g OGTT should be performed when patient is fasting. The diagnosis of GDM is made if at least 2 of the following 4 plasma glucose levels are met or exceeded:

Carpenter/Coustan

- Fasting 95 mg/dL
- 1-hour 180 mg/dL
- 2-hour 155 mg/dL
- 3-hour 140 mg/dL

HbA1C, fasting plasma glucose, 1-hour plasma glucose, 2-hour plasma glucose had been shown to be predictor of preeclampsia.

Fetal growth restriction is defined as a customized birthweight <10th centile for gestational age [31].

Preterm labor is defined as is the [birth](#) of a [baby](#) at less than 37 weeks [gestational age](#) [31, 32]

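### Composites 1 and 2 use a hypertension term defined to include the chronic hypertension for which women are enrolled; narrower terms elsewhere conflict with it, and nothing says which governs

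*Protocol*

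**What the plan says.** Protocol section 3.7.2 introduces the composites with "Pregnancy complication listed as composite endpoints below". Composite 1 is hypertensive disorder of pregnancy and nothing else; composite 2 is "hypertensive disorder of pregnancy or preterm labor or fetal growth restriction". The individual outcomes include "incidence of hypertensive disorder of pregnancy". Section 3.9.2 repeats the term, again without qualification.

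Section 2.1 supplies the definition: "Hypertensive disorder of pregnancy consisted of 4 categories". They are (a) pre-eclampsia-eclampsia; (b) chronic hypertension, which "is hypertension that predates pregnancy"; (c) superimposed pre-eclampsia, which "is chronic hypertension in association with preeclampsia"; and (d) gestational hypertension. Section 3.2.1 makes chronic hypertension before pregnancy the first of five alternative high-risk entry conditions, and hypertension before 20 weeks the second.

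Other places use narrower language. The research question in section 1.2 asks whether CPAP can "reduce related maternal and fetal complications". The secondary objective in section 1.3.2 is "To compare the composite outcome of pre-eclampsia/GHT, GDM, fetal growth restriction, and pre-term labor between the CPAP treatment and control groups". The Protocol Flow Chart has a PIH/preeclampsia event row marked in the second trimester, the third trimester and at delivery, but not at enrollment.

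Section 3.10.4 takes gestational diabetes out of the endpoint analyses because it is an inclusion criterion. It has no matching sentence for hypertension.

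**The concern.** An endpoint should be something that can still happen after randomisation. Here the defined term covers a condition that some women have on entry and for which they are selected. An analyst who looks up the term in section 2.1 would count those women as events from the start; one who follows the objective or the flow chart would not. Two competent analysts could therefore report different event counts for composites 1 and 2 and for the individual outcome, in a trial that is open-label.

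The removal of gestational diabetes makes this matter more. In the Combined protocol and SAP, composite 1 was hypertensive disorder or gestational diabetes. In the Protocol it is hypertensive disorder alone, so the ambiguous term is the whole endpoint. Section 3.10.4 also plans logistic models for predictors of these outcomes; under a literal count, chronic hypertension would predict composites 1 and 2 perfectly.

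**Working it through.** **1. Apply the definition to one woman.** She enters under criterion (a) with chronic hypertension.

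| Source | Her status at entry | If superimposed pre-eclampsia follows |
|---|---|---|
| Sections 2.1 and 3.7.2, literally | Event, category (b) | Still an event; no change |
| Section 1.3.2 (pre-eclampsia or gestational hypertension) | Not an event | Event, if superimposed disease counts as pre-eclampsia (not stated) |
| Flow chart event row | Not recorded at enrollment | Recorded if classed as pre-eclampsia |

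Under the literal reading she is also already an event for composite 2, so preterm birth or growth restriction adds nothing.

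**2. Deleting category (b) alone is not enough.** Section 2.1 describes category (d) as raised pressure after 20 weeks without proteinuria or systemic findings. It does not require normal pressure beforehand. A woman whose chronic hypertension persists past 20 weeks could be read into (d), so the clarification must refer to hypertension at entry.

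**3. Effect on the risk difference.** Let q be the share with chronic hypertension, d_C the risk difference for new-onset events in those women, and d_N the difference in the others.
- New-onset counting: D = q·d_C + (1−q)·d_N
- Literal counting: D_lit = (1−q)·d_N, because women with chronic hypertension are events in both arms
- Fraction retained = D_lit / D, which equals (1−q) only if d_C = d_N

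With q = 20% assumed and D = 15 points:
- d_C = d_N = 15: 0.8 × 15 = 12 points, 0.80 retained
- d_C = 30, d_N = 11.25: 0.8 × 11.25 = 9 points, 0.60 retained
- d_C = 0, d_N = 18.75: 0.8 × 18.75 = 15 points, 1.00 retained

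The documents give neither q nor the two effects. Section 1.1.3 argues against assuming equal effects: it reports apparent prevention of pre-eclampsia in women with chronic hypertension, but not in women with pre-eclampsia risk and obesity.

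**4. The plan's own figures, and an illustration.** I used the pooled-variance comparison of two proportions, two-sided 0.05:
- n per arm = [1.96√(2p̄(1−p̄)) + 0.8416√(p₁(1−p₁)+p₂(1−p₂))]² / (p₁−p₂)²
- power = Φ{[|p₁−p₂|√n − 1.96√(2p̄(1−p̄))] / √(p₁(1−p₁)+p₂(1−p₂))}

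Composite 1: 33.5% vs 18.5% gives 133.05, rounded up to 134 per arm, as stated in section 3.9.2. Composite 2: 21.4% vs 6.4% at 153 per arm gives power 0.970, stated as 0.97.

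Replacing each rate p by q + (1−q)p, which assumes equal effects, gives power at 153 per arm of:

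| Assumed q | Difference (points) | 21.4% vs 6.4% | 33.5% vs 18.5% |
|---|---|---|---|
| 0 | 15.0 | 0.97 | 0.85 |
| 10% | 13.5 | 0.81 | 0.71 |
| 20% | 12.0 | 0.62 | 0.57 |
| 30% | 10.5 | 0.47 | 0.45 |

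These figures show direction only. The rates 18.5% and 21.4% come from the Combined protocol and SAP, for composites that included gestational diabetes; the Protocol states no rate for its composites 1 and 2. Section 3.9.2 adds emergency caesarean section to composite 2, which section 3.7.2 does not. The 153 per arm is out of date: Protocol section 3.9.1 gives 167, at which q = 20% yields 0.66 and 0.61.

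**The case against.** The best defence is that new-onset events were plainly meant. The objective names the hypertensive component as pre-eclampsia or gestational hypertension, the event row starts after enrollment, and section 3.7.2 speaks of complications and incidence. On this view section 2.1 is a general classification, not an endpoint rule. The authors also reviewed overlap with the inclusion criteria when they removed gestational diabetes, and kept hypertension, which fits a new-onset understanding as well as an oversight.

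Much of this stands. A reader might infer that the plan is silent on new-onset disease; it is not, because the objective does use narrower terms. A reader might also infer that women with chronic hypertension have been or will be counted as events; nothing shows that. What remains is a conflict. The objective still lists gestational diabetes and matches no current composite, neither it nor the flow chart is tied to composites 1 or 2, and neither says how a woman hypertensive at entry is counted. The endpoint section uses the one term that the plan formally defines, and that definition includes her.

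A reader might further infer a specific loss of power, or a bias towards one arm. The documents support neither. The power figures rest on an unknown q, superseded rates and an assumed equal effect. Under randomisation, events already present at entry are expected in both arms alike.

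**Conclusion.** Wrong as written, and worth fixing, with medium confidence that it would affect the analysis, since the context favours the new-onset reading. Followed literally, the definition counts every woman with chronic hypertension as an event at baseline, hides superimposed pre-eclampsia, and removes from the comparison any benefit of CPAP in those women. If CPAP helps them, the overall difference is diluted; the amount cannot be computed from the documents. The factor (1−q) is exact only if the risk difference is the same with and without chronic hypertension. Only composites 1 and 2 and the individual hypertensive outcome, all secondary, are affected. Composite 3 names severe pre-eclampsia or eclampsia rather than the broad term, and the primary blood-pressure outcome does not use it.

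**What to change.** Issue a dated clarification, written without sight of event counts by arm, that reconciles sections 1.3.2, 2.1, 3.7.2, 3.9.2 and the flow chart. It should state that, for composites 1 and 2 and the individual outcome, the hypertensive component is any of:
- pre-eclampsia or eclampsia
- superimposed pre-eclampsia
- gestational hypertension in a woman without hypertension at entry

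It should add that hypertension present at entry, by either hypertensive inclusion route, is a baseline characteristic and not an event.

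The cost is a short statement placed in 3.7.2 and repeated in 3.9.2. No new data or visits are needed: underlying disease and blood pressure are recorded at the first visit (section 3.6.1.1), and hypertensive events are scheduled after enrollment. The date and blinding matter because the Protocol runs enrollment to October 2019 and already reports some conduct in the past tense. If new-onset counting was used all along, the clarification simply documents it.
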